## ENGAGES One-Year Outcomes Analysis Plan

Analyses to be completed using R software.

All tests to be 2-sided. P values < 0.05 to be considered suggestive, and P values < 0.005 to be considered as stronger evidence.

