### ***Hypothesis 2: Is EEG Guidance Intervention Associated with Improved Quality of Life One Year After Surgery?***

*Patient Population:* Patients randomized to intervention or control (N = 1232)

*Primary Predictor Variable:* EEG guidance intervention

(X=0 for control or X=1 for intervention)

Intention to treat

*Outcomes:* Veterans RAND 12-Item Health Survey (VR-12) physical component score (PCS), VR-12 mental component score (MCS), one year postoperatively

- Partially completed VR-12 surveys will not be scored and will be considered missing.

*Data Description Plan:* Box plots of VR-12 PCS and MCS at baseline, 30 days, and 1 year for the two groups. Provide median, interquartile range, and range at each time point.

*Analysis Plan:* Generalized linear model

$$y_{365} = \beta_0 + f(y_0) + \beta_1 x + \beta Z + \varepsilon$$

- In this equation,  $y_{365}$  is the quality of life (either VR-12 PCS or VR-12 MCS) at one year, and  $y_0$  is the quality of life metric at baseline.  $x$  is the EEG guidance intervention ( $x=0$  for control or  $x=1$  for intervention).  $Z$  is a vector of additional variables for which we will adjust.
- $f(y_0)$  is a potentially nonlinear function describing the relationship between baseline quality of life and quality of life at one year. This function will be modeled using splines.
- Will perform unadjusted ( $Z = \text{null}$ ) and adjusted ( $Z$  not null) analyses. Will adjust for age, sex, American Society of Anesthesiologists (ASA) physical status classification (1-2 vs 3 vs 4-5), number of comorbid conditions, baseline poor functional capacity (<4 METS), history of falls (yes/no within previous 6 months), evidence of abnormal cognition (preoperative Short Blessed Test score > 4), surgery type (cardiac versus non-cardiac), length of anesthesia (Anesthesia Stop – Anesthesia Start)
  - o Multiple imputation may be performed to address missing values of these variables
- Any patient with missing quality of life either at baseline or at one year will be excluded.
- $H_0: \beta_1 = 0$  (The null hypothesis is that the EEG guidance intervention has no association with postoperative quality of life.)

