9. Is median intraoperative end-tidal anesthetic concentration value (measured in MAC) associated with more falls at one year?
  - a. Logistic regression, adjusting for same variables as in hypothesis #3
  - b. Instrumental variable analysis will be used to account for the EEG intervention
10. Is the EEG guidance intervention associated with higher (better) Barthel Index at one year?
  - a. Will only be available for patients who return the SATISFY-SOS survey
  - b. Mann Whitney U test (because we expect a skewed distribution)
11. Is the EEG guidance intervention associated with a higher rate of return to work at one year?
  - a. Will only be available for patients who return the SATISFY-SOS survey
  - b. Chi-square test for dichotomous return to work (yes/no)
  - c. Among patients who return to work, Mann Whitney U test for number of months before the patient returned to work

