Because a history of falls in older adults is associated with increased fall risk⁷¹ the research staff may recommend and provide (if acceptable to patients and if patients live <45 miles from the hospital) home occupational therapy visits that have the general aim of improving daily activity performance/safety and prevention of falls. Because delirium in older adults is associated with increased fall risk⁷²⁻⁷⁶ the research staff will recommend that patients' families exercise increased vigilance when delirium features are noted in the hospital or after hospital discharge. Patients and their families will also be reminded about the home safety assessment tool that they received at the time of enrollment (Appendix: See CDC Fall Safety Information Sheet).

Data Collection

Baseline assessment will take place at the CPAP clinic and include demographic information, a detailed medical history, physical examination, assessment of preoperative quality of life, and evaluation of falls history. Delirium will be assessed daily in the postoperative period of the hospital stay. Data collected specifically for the ENGAGES study, such as the daily delirium assessments, will be entered into the Washington University School of Medicine Research Electronic Data Capture (REDCap) application.⁷⁷ In the ENGAGES study, EEG data (including BIS values and EEG burst suppression durations) will be collected in the intervention group as well as in the blinded control group.^{36,50} Furthermore, perioperative data (including repeated measures data) will be retrieved from the hospital's perioperative electronic medical record (Metavision by iMDsoft®, Needham, MA).^{36,41,53,78} We are able routinely to capture high fidelity perioperative data from our MetaVision to an SQL server (Microsoft, Redmond, WA) database. Routinely acquired data include detailed patient medical history, surgical history, specific patient risk factors, medications, Barthel Index, VR-12 quality of life data, Short Blessed Test, sleep apnea screening, laboratory data, intraoperative medications, physiological readings, and postoperative recovery parameters. Olfaction might be assessed preoperatively with the Brief Smell Identification Test, as hyposmia has been identified as a risk factor for postoperative delirium.⁷⁹ All the data for SATISFY-SOS are integrated from various data sources and are stored in a single data repository housed in the Department of Anesthesiology at Washington University.

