Cognitive Testing

When patients are assessed for delirium, structured cognitive appraisal is performed, which gives the interviewer an opportunity to make observations that are used when scoring the CAM. In addition, as part of the routine preoperative assessment, patients will be screened for cognitive impairment with the AD-8 dementia screen⁸⁰ and with the Short Blessed Test.⁸¹ Tests from the cognitive battery of the NIH toolbox might also be incorporated in the baseline assessment.^{82,83} This computer based battery assesses Executive Function, Attention, Episodic Memory, Language, Processing Speed and Working Memory (See Appendix). Depending on time constraints, patients might complete a long form of the cognitive battery or a version focused on executive function, episodic memory and attention. Patients who prefer not to do computer based cognitive tests will be offered paper based cognitive tests (Trails A and B, and Stroop Color and Word Test). Impaired performance on preoperative cognitive tests is reportedly associated with postoperative delirium^{84,85}, and postoperative delirium has been found to be associated with persistent postoperative cognitive decline.¹⁸ Therefore, when patients are followed up postoperatively at thirty days, the Short Blessed Test will be administered on the telephone. When patients are followed up postoperatively at one year, the Short Blessed

(hematocrit <35%), functional status, 6 months history of falls and the Barthel Index.⁸⁶ In addition to these measures, for the ENGAGES study we plan to measure grip strength and the Timed Up and Go (TUG) test.⁸⁶ Grip strength will also be assessed with three measurements in the dominant hand using a Jamar® handheld dynamometer (Lafayette Instruments, Lafayette, IN).⁸⁷ Maximal grip strength will be selected for analysis.

Patients' Postoperative Health and Wellbeing

All patients enrolled in the ENGAGES study will already have provided informed consent for the SATISFY-SOS study. Using the SATISFY-SOS infrastructure, the ENGAGES study will track postoperative patient reported outcomes at approximately 1 month and at 1 year. Patient reported outcomes tracked include health-related quality of life and postoperative falls.

Outcome Measures

i) Incidence of Postoperative Delirium (Aim 1 in Figure 2)

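### The exploratory one-year Barthel comparison is valid, but it gives up some power by ignoring baseline Barthel and the stratification factors

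*SAP*

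**What the plan says.** Item 10 of the SAP's Exploratory Analyses asks "Is the EEG guidance intervention associated with higher (better) Barthel Index at one year". It limits the data: "Will only be available for patients who return the SATISFY-SOS survey". The whole analysis is a "Mann Whitney U test (because we expect a skewed distribution"). There is no baseline term, covariate list or stratification.

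The protocol, under Data Collection, states: "Routinely acquired data include detailed patient medical history, surgical history, specific patient risk factors, medications, Barthel Index, VR-12 quality of life data, Short Blessed Test". A later paragraph, on measures to which grip strength and the Timed Up and Go test are added, names "functional status, 6 months history of falls and the Barthel Index". The start of that paragraph is cut off in the text available, so its preoperative meaning is read from context.

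Elsewhere the plan does adjust:
- Hypothesis 2 models one-year VR-12 with a spline in its own baseline, a term that "is a potentially nonlinear function describing the relationship between baseline quality of life and quality of life at one year".
- Sensitivity analysis 5 of Hypothesis 3 (number of falls, also from the SATISFY-SOS one-year survey) is an ordinal logistic regression with covariates.
- The protocol's Randomization and Blinding section stratifies 1:1 allocation by cardiac surgery and by falls within six months, giving four strata.

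**The concern.** The stated reason for the Mann-Whitney test is skew. Skew supports a rank-based or ordinal method, but such methods can carry a baseline covariate, and the SAP already uses an adjusted ordinal model for number of falls. The reason given therefore does not explain why a baseline score listed as routinely acquired is left out, or why the two stratification factors are.

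What is at stake is precision. If one-year Barthel correlates with its preoperative value, an unadjusted comparison leaves explainable variation in the error term. The analysis set is also smaller than the trial. The protocol plans on about 80% one-year completion but reports about 66% response in the SATISFY-SOS cohort. The SAP reads p-values at two levels ("P values < 0.05 to be considered suggestive, and P values < 0.005 to be considered as stronger evidence"), and lost precision costs more at the stricter one.

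**Working it through.** **No figure to reproduce.** The documents give no power, effect size, SD, baseline correlation or ceiling share for Barthel. Everything below on size is illustration under stated assumptions.

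**Inputs from the documents.** N = 1,232, allocated 1:1 (SAP Hypothesis 1; protocol, Randomization and Blinding). One-year response about 66% (protocol, Strengths and Limitations): 0.66 × 1,232 = 813, about 407 per arm. Two-sided tests at 0.05 and 0.005 (SAP opening section).

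**Assumed inputs.** Correlation of baseline with one-year score, share of patients at the maximum score, and treatment effect.

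**Step 1: formula, no ceiling.** Adjusting for a baseline with correlation ρ multiplies residual variance by 1 − ρ². For a comparison with 80% unadjusted power at two-sided 0.05, adjusted power = Φ((1.960 + 0.842)/√(1 − ρ²) − z), with z = 1.960 at the 0.05 level. The equivalent sample-size multiplier is 1/(1 − ρ²).

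| ρ | N multiplier | Power at 0.05 | Power at 0.005 |
|---|---|---|---|
| 0 | 1.00 | 80.0% | 49.8% |
| 0.2 | 1.04 | 81.6% | 52.1% |
| 0.3 | 1.10 | 83.6% | 55.2% |
| 0.5 | 1.33 | 89.9% | 66.6% |
| 0.7 | 1.96 | 97.5% | 86.8% |

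Here ρ is the correlation on the scale analysed. A ceiling lowers it, so this table overstates the gain for a score with many patients at the maximum.

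**Step 2: simulation with a ceiling.** Scores were built from correlated normal variables in 5-point steps capped at 100. The tie-corrected Mann-Whitney test was compared with a regression of one-year ranks on arm and baseline ranks, at two-sided 0.05. With 407 per arm, a latent effect of 0.20 SD and 3,000 trials per scenario, power (unadjusted → adjusted) was:

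| At ceiling | Latent correlation 0.3 | 0.5 | 0.7 |
|---|---|---|---|
| 50% | 65.8 → 67.7% | 66.3 → 74.2% | 65.7 → 81.9% |
| 70% | 51.6 → 53.4% | 53.1 → 57.2% | 50.8 → 63.0% |
| 80% | 41.9 → 42.2% | 42.3 → 44.6% | 42.9 → 50.9% |

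The gains are 0.3 to 1.9 points at 0.3, 2.3 to 7.9 at 0.5, and 8.0 to 16.2 at 0.7.

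With a latent effect of 0.22 SD and 2,000 trials per scenario:

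| At ceiling | Latent correlation 0.5 | 0.7 |
|---|---|---|
| 50% | 78 → 86% | 79 → 93% |
| 60% | 74 → 81% | 74 → 89% |
| 70% | 67 → 73% | 69 → 81% |
| 80% | 58 → 62% | 61 → 71% |

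At correlation 0.3 the gain was about 1 to 3 points at every ceiling share. A repeat with 1,500 trials gave 79 → 82% (50% at ceiling), 68 → 70% (70%) and 57 → 58.5% (80%) at 0.3, and 77 → 94% at 0.7 with 50% at ceiling. Over the repeated runs at 0.22 SD the gains span about 1–3, 4–8 and 9–17 points for correlations 0.3, 0.5 and 0.7.

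**Step 3: validity.** With no treatment effect, rejection rates were 4.7% (Mann-Whitney) and 5.0% (adjusted) in the 0.20 SD set-up, and 4.9–5.7% and 4.7–5.3% in the 0.22 SD set-up. Both tests hold their level.

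**Step 4: why missing baselines matter.** In the first simulation the observed rank correlation was 0.175 (latent 0.3, 70% at ceiling) and 0.275 (latent 0.5, 80% at ceiling). Dropping a fraction f of responders cancels the gain when (1 − f)/(1 − r²) = 1, that is, f = r²: 0.175² = 3.1% and 0.275² = 7.6%. Excluding patients without a baseline score could therefore remove the whole benefit.

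**Not covered.** These runs adjust for baseline ranks only. No gain was computed for the stratification factors or for the proportional-odds model itself.

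**The case against.** The strongest case for leaving item 10 alone is that it is one of eleven exploratory analyses, has no power target and feeds no main conclusion. The planned test is simple and holds its level, and item 11 is also unadjusted. A proportional-odds model adds an assumption. Most of this stands, and it sets the priority. It does not make skew a reason to omit baseline.

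The size is also open to challenge. A correlation of 0.5 to 0.7 has no support in the documents. At 0.3, or with most patients at the ceiling, the gain is a point or two and can be close to zero. That stands.

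Availability is not certain either. The Data Collection list mixes preoperative, intraoperative and postoperative items, the related paragraph is truncated, and completeness of baseline Barthel is stated nowhere. A preoperative reading is plausible, but a rule for missing values is needed.

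A reader might infer that the planned test is biased, or that chance imbalance at baseline invalidates it. The documents do not support that: allocation is randomised and stratified, and the type I error already allows for chance imbalance. A reader might also expect baseline adjustment to cure selective survey return. It can address only the part carried by measured baseline function.

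**Conclusion.** Item 10 is a valid analysis that is less efficient than one the trial could probably run on data it already collects. For 813 responders and an assumed latent effect of 0.22 SD with 50–80% at ceiling, the loss is about 1–3 power points at latent correlation 0.3, about 4–8 at 0.5 and about 9–17 at 0.7. It tends to shrink as the ceiling share rises, and is slightly smaller at 0.20 SD. The direction is secure whenever baseline and one-year scores correlate and baseline is nearly complete. The size is not secure, because correlation, ceiling share and effect are all assumptions.

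It would be tempting to report a large, known loss of power. The documents give nothing from which to derive one, and the upper figures need a strong correlation that they do not state. No main one-year conclusion is affected. Low priority.

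**What to change.** Replace item 10b with a proportional-odds (ordinal logistic) model of one-year Barthel on arm, baseline Barthel and the two stratification factors (cardiac surgery, falls history). This matches the ordinal model the SAP already plans for number of falls. Name it as the analysis for item 10, and report the Mann-Whitney test as its unadjusted companion.

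Keep responders with no baseline Barthel in the analysis by imputing the baseline value. Either the stratum mean, as in the Hypothesis 2 missing-data scenarios, or multiple imputation, which the SAP already allows for covariates, would serve; choose one in advance. Confirm first that the stored Barthel score is preoperative and how complete it is.

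The cost is a few lines in the SAP, slightly more analysis work and a proportional-odds assumption that should be examined. No new data collection is needed if the preoperative score is held as the protocol indicates.

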### ***Hypothesis 1: Is EEG Guidance Intervention Associated with Reduced One-Year Mortality?***

*Patient Population:* Patients randomized to intervention or control (N = 1232)

*Primary Predictor Variable:* EEG guidance intervention

(X=0 for control or X=1 for intervention)

Intention to treat

*Outcome:* Mortality, with one-year follow up

- Any patient who is lost to follow up before one year will be right-censored at the time of last follow-up. (No assumptions are made about vital status after the date of last follow up.)

*Data Description Plan:* Kaplan-Meier curves, stratified by intervention group

*Analysis Plan:* Cox proportional hazards regression for one-year mortality

- Will perform unadjusted and adjusted analyses
- Will adjust for age, sex, American Society of Anesthesiologists (ASA) physical status classification (1-2 vs 3 vs 4-5), number of comorbid conditions, baseline poor functional capacity (<4 METS), history of falls (yes/no within previous 6 months), evidence of abnormal cognition (preoperative Short Blessed Test score > 4), surgery type (cardiac versus non-cardiac), length of anesthesia (Anesthesia Stop – Anesthesia Start)
  - o Multiple imputation may be used to address missing values of these variables

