Randomization will be performed at the patient level using computer-generated assignment. Eligible patients who provided written informed consent will be randomized to receive the intraoperative electroencephalography-guided protocol or routine care. In order to ensure that there is not major imbalance between group assignments with respect to history of falls and cardiac surgery, subjects will be randomized (1:1) between the EEG-guided and routine care groups in blocks of 20 within these four strata (i.e., cardiac surgery with a history of falls within 6 months, cardiac surgery without a history of falls within 6 months, non-cardiac surgery with a history of falls within 6 months; and non-cardiac surgery without a history of falls within 6 months). Trained members of the research team will enroll participants and will implement the assignment of participants to the EEG-guided or usual care protocols. Group assignment will be revealed to members of the anesthetic team only when the patient enters the operating room by opening a sequentially numbered, opaque, sealed envelope in a sequence generated by one of the study's data analysts. Patients and their families will be blinded to group allocation and different members of the research team will assist with the intervention in the operating room (will not be blinded to the intervention) from those conducting the postoperative assessments (will be blinded to the intervention).^{51,52} To reduce predictability of a random sequence, details of patients already randomized and prior group assignments will be recorded in a separate document that is unavailable to those who enroll participants and assign interventions.

Primary Intervention – EEG-guided Anesthetic Protocol

The primary intervention to which patients will be randomized in this study is a pragmatic EEG-guided anesthetic protocol (See Appendix). All anesthesia practitioners will receive a targeted educational session on recognition of EEG patterns typically occurring during general anesthesia. The content will be similar to that described in an article where we demonstrated that anesthesiologists could estimate BIS (processed EEG

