Our sample size calculations are based on the anticipated delirium incidence and effect size for our primary endpoint analysis. Based on results of a previously published meta-analysis of four studies investigating the use of BIS-guided anesthetic administration, we conservatively assume an incidence of postoperative delirium in the routine anesthesia care group of 25%.²⁹ We performed a sample size sensitivity analysis and calculated different scenarios with different values for the delirium incidence in the intervention arm and corresponding power (80%, 90%, and 95%). With a two sided alpha $<5\%$ and 1,232 patients (616 per arm), the trial will have $>95\%$ power to detect an absolute decrease in delirium incidence $\geq 9\%$, $>90\%$ power to detect a decrease in delirium incidence $\geq 8\%$, and $>80\%$ power to detect a decrease in delirium incidence $\geq 7\%$. With a 7% decrease in delirium incidence, the 95% confidence interval would be approximately 3% to 12%. Even a 3% decrease in delirium incidence would be clinically important, suggesting that delirium would be prevented in one out of every 33 at risk patients who received EEG-guidance of general anesthesia.

ii) Health Related Quality of Life

The overall sample size of our study is defined through estimations of the primary outcome (delirium). For secondary analyses, we assume that ~80% of our trial population (~1,000 participants) will have completed the trial and the 1-year follow-up survey. With this sample size of 1,000, we can detect a difference of 0.5 points (standard deviation of 2.5) in the mean change of Physical Health Score from baseline to 1 year between the intervention and usual care group with a power of $>80\%$ and a two-sided alpha level of $p<0.05$.

iii) Postoperative Falls

This calculation is similarly based on the assumption that ~80% of our trial population (~1,000 participants) will have completed the trial and the 1-year follow-up survey. Based on a study that showed a preoperative fall prevalence of 33% over six months preoperatively in a similar patient population to the ENGAGES trial, we will conservatively assume an incidence of postoperative falls at 1-year in the routine anesthesia care group of 40%.¹¹⁰ With a sample size of 1,000, we will have $>80\%$ power to detect an absolute risk reduction of 12% between the EEG-guided and the usual care group at a two-sided alpha level of $p<0.05$.

Analysis of Pragmatic Elements of the ENGAGES Study

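### SAP exploratory item 11c tests months to return to work only among patients who returned, a subset formed after randomisation, so it can mislead in either direction

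*SAP*

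**What the plan says.** Item 11 of the SAP's Exploratory Analyses asks: "Is the EEG guidance intervention associated with a higher rate of return to work at one year". It has three parts.

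- **11a** limits the data: "Will only be available for patients who return the SATISFY-SOS survey".
- **11b** is a chi-square test of return, yes or no.
- **11c** reads: "Among patients who return to work, Mann Whitney U test for number of months before the patient returned to work".

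Patients who had not returned by the survey do not enter 11c. The item has no censoring, no rank for non-returners and no rule for reading 11c together with 11b. It does not say whether patients who were not working before surgery count as a no in 11b. No other section of either document analyses time to return in all patients. The SAP does use Kaplan-Meier curves and Cox regression with right-censoring, but for mortality (Hypothesis 1).

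The general rule at the head of the SAP is: "All tests to be 2-sided. P values < 0.05 to be considered suggestive, and P values < 0.005 to be considered as stronger evidence".

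**The concern.** Randomisation makes the two arms comparable as a whole. It does not make the returners in one arm comparable with the returners in the other, unless the intervention leaves the decision to return untouched. Item 11b exists because the investigators think it may not.

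Suppose the intervention lets some patients return who otherwise would not have done so. They enter the intervention arm's 11c sample, and their counterparts in the control arm are left out. If they tend to return late, the intervention's months shift upwards although no patient was slowed. If instead the intervention stops some late returns, the slow patients drop out of its sample and it looks faster. At stake is an exploratory P value below 0.05 that points the wrong way and that the SAP would have readers call suggestive.

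**Working it through.** The documents give no return rate, timing, effect size or power for return to work, so there is no planned figure to reproduce. Everything below except the survey-response figures is an assumption, used to show the mechanism and its range.

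**How many workers could there be?** The protocol's Sample Size Calculations section says "we assume that ~80% of our trial population (~1,000 participants) will have completed the trial and the 1-year follow-up survey". Its Strengths and Limitations section gives about 66% response in SATISFY-SOS. With 1,232 patients randomised 1:1:

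- at 80%: 1,232 × 0.80 / 2 ≈ 493 responders per arm
- at 66%: 1,232 × 0.66 / 2 ≈ 407 responders per arm

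Thus 150 workers per arm would be 30% to 37% of responders, and 50 per arm would be 10% to 12%. The documents do not say how many patients worked before surgery.

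**Worked example (assumed), 120 workers per arm.** In the control arm 60 return, 10 in each of months 1 to 6. The intervention arm has the same 60, plus 20 who would otherwise not have returned, 4 in each of months 8 to 12. No patient is worse off.

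- *11b:* 80/120 against 60/120, or 67% against 50%. Chi-square = 240 × (80×60 − 40×60)² / (120 × 120 × 140 × 100) = 6.86, p = 0.009, favouring the intervention.
- *11c:* control mean 3.5 months; intervention mean (60×3.5 + 20×10)/80 = 5.1 months; medians 3.5 and 4.5. Of 80 × 60 = 4,800 pairs, counting ties as half, the intervention patient is later in 1,800 + 1,200 = 3,000, or 62.5%. Mann-Whitney p = 0.011, against the intervention.
- *Non-returners kept, worst rank:* of 120 × 120 = 14,400 pairs, the intervention patient is worse in 1,800 + 1,200 + 2,400 + 1,200 = 6,600, or 46%. p = 0.25, leaning towards the intervention.
- *Non-returners kept, log-rank with censoring at 12 months:* z = 1.91, p about 0.056, towards the intervention.

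**Simulation (assumed).** Control return is 60%, and other returners are spread evenly over months 1-6. No worker is slowed; the intervention only adds returners. The table shows how often 11c finds the intervention significantly slower at two-sided p < 0.05, with 150 workers per arm.

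| Gain in return | Timing of extra returners | 11c against intervention |
|---|---|---|
| 10 points | months 1-6, as for others | about 2.5% (nominal) |
| 5 points | months 1-12 | about 7% |
| 5 points | months 7-12 | about 14% |
| 10 points | months 1-12 | about 15% |
| 10 points | months 7-12 | about 42% |

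In the last row the expected means are 3.5 months and (60×3.5 + 10×9.5)/70 = 4.4 months; at p < 0.005 the rate is about 13%. With 50 workers per arm, the two months 7-12 scenarios give about 8% (5 points) and 16-17% (10 points). At 150 per arm, the Mann-Whitney test over all workers, with non-returners ranked last, is significantly against the intervention in about 1% or less.

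**The other direction.** Exchange the arm labels in the last row: the intervention now lowers return from 70% to 60% by removing late returners. By symmetry 11c then finds it significantly faster in the same 42% of trials, although fewer patients returned.

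**No effect on return.** With equal return rates and timing, 11c keeps its level: about 4-6% in total over both directions.

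**The case against.** The strongest reply is that little rests on 11c. It is the last part of the last of eleven exploratory items. Return to work is not among the outcomes listed in the protocol and has no sample-size calculation. Item 11b answers the stated question without conditioning on return, and 11c states its condition openly. A result that more patients returned and that returners took longer is not a contradiction. This stands, and it limits the impact.

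It does not remove the problem. At 150 per arm in the 10-point, months 7-12 scenario, 11b favours the intervention at p < 0.05 in only about 45% of trials. In about 24% of trials 11c is significantly against the intervention while 11b is not significant, so 11c would be the only signal from the item.

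A second reply is that 42% comes from a near-extreme scenario, in which every extra returner comes after all the others. That also stands. A reader might infer that 11c is biased towards harm, or that a false harm is the expected result. The documents support neither: they say nothing about when extra returners would come back, and the direction can reverse. If half of the other returners came back one month sooner, the 42% falls to about 4%.

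A third reply is that survey responders are themselves a subset formed after randomisation. This is correct. Keeping non-returners removes the conditioning on return, not the restriction in 11a.

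**Conclusion.** The point holds in a limited form. Item 11c is not a randomised comparison whenever the intervention affects who returns, and its P value can then point the wrong way, for or against the intervention. The rate of wrong-direction significance runs from nominal (about 2.5%) to about 42% at 150 workers per arm. It depends on the assumed gain, the timing of the extra returners and the number of workers, none of which the documents give. If the intervention does not affect who returns, this conditioning does no damage.

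A reader might go further and treat the one-year conclusions as threatened. They are not: mortality, quality of life and falls do not use this analysis. It remains worth correcting because the change is small and 11c as written does not answer the question that item 11 asks.

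**What to change.** Replace the test in 11c with a comparison of time to return that keeps non-returners, among survey responders who were working before surgery. Choose one method in advance:

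- log-rank test or Cox regression, with non-returners censored at the survey date; or
- Mann-Whitney test with non-returners given the worst rank, which keeps the test already named in the SAP.

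Show months among returners descriptively only, labelled as conditional on return. Apply the same working-before-surgery restriction to 11b, so that people who had no job to return to are not counted as failures. State where preoperative working status comes from, since I found no source named in the documents.

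The cost is SAP wording. Return and months come from the survey answers already planned; only preoperative working status needs a source. There are two downsides. The result is no longer a simple median among returners, and the restriction to survey responders in 11a remains and should be stated as a limitation.
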